4. Participants will receive their assigned injection. Participants who are randomized to the placebo group will receive an injection of 7cc of sterile saline. Participants who are randomized to the corticosteroid group will receive an injection of 2cc (80mg) of Kenalog®-40 (triamcinolone acetonide injectable suspension, USP) mixed with and 5 cc of 1% plain lidocaine for a total of 7cc of fluid injected. Kenalog® injections are part of the current standard of care for patients with osteoarthritis of the knee. Participants who are randomized to the Lipogems® treatment group will undergo a lipoaspiration from their abdomen and autologous injection of the harvested adipocytes into their knee. It is standard to harvest three to four times more adipose tissue than is planned to be injected to account for tissue processing by the Lipogems® device. We plan to inject 7cc of autologous adipose tissue. Thus, we will harvest between 25 and 30 cc of adipose tissue from each patient. The tissue will be processed immediately and 7cc will be injected. Any remaining adipose tissue will be disposed of immediately in biohazardous waste. Lipogems® is currently approved for orthopedic and arthroscopic procedures; thus, this would be an on-label use. All injections will be performed in the clinic by [name], [name], and [name] PA-C as an in-office procedure.
5. Participants will be scheduled to return for in-person follow-up visits with a research staff member at 6 weeks and 6 months after their injection, where they will again complete a medication log, Western Ontario and McMaster Universities Osteoarthritis Index, a VAS pain scale, and the Knee Injury and Osteoarthritis Outcome Score scales. They will also complete the above surveys and log at 2 weeks, 3 months, and 1 year post injection, but these will be completed online. The above mentioned surveys and medication log will be generated in RedCap and emailed securely to participants for their completion. If participants do not have email or access to the internet, these surveys will be completed over the phone and entered into RedCap by research staff.
6. Upon completion of their 1-year questionnaires, participants who were randomized to receive Lipogems® or Corticosteroid injections will be finished participating in the study.

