- 14.4. *The existing literature has been reviewed regarding Lipogems®. A board certified plastic surgeon was consulted regarding adverse effects of lipoaspiration procedures and the adverse risks are detailed in this protocol and the consent form.*
- 14.5. *N/A. Safety data is not collected in this study.*
- 14.6. *The research will be suspended and/or terminated if there is an unexpected serious adverse event that requires further investigation.*

15. Withdrawal of Subjects

- 15.1. *We do not anticipate any medical reasons to withdraw subjects from the study without their consent. If participants are not adherent and miss follow-up appointments, refuse to be scheduled, or do not respond to scheduling requests, they will be withdrawn from the study.*
- 15.2. *Participants may withdraw at their request and continue to seek standard of care treatments with the physician of their choice. No labs/tapering of meds/or physical exams are necessary to withdraw.*
- 15.3. *Partial withdrawal will be permitted if a patient desires to continue participating in data collection but no longer wishes to be seen for follow-up. The questionnaires would be completed online only. All previously collected data will still be used for research purposes unless the patient explicitly asks for data to be excluded.*
- 15.4. *If a patient withdraws, all previously collected data will still be used for statistical analysis unless the participant explicitly asks for their previous data to be excluded from further consideration. Describe the disposition of existing data/specimens when a subject withdraws.*
- 15.5. *If a patient requests to be withdrawn, [name], the principal investigator, must be made aware. If the patient requested that their data be destroyed and not used for analysis, then the data will be properly destroyed. Otherwise, data that was collected prior to withdrawal from the study may be used for analysis.*

16. Data Management/Confidentiality

- 16.1. *Members of the research team will be permitted to access the participants' medical records through PowerChart to confirm participant eligibility and document procedures and follow-up visits. PHI will be reviewed as part of the normal screening process in clinic.*
- 16.2. *Members of the research team will have access to direct identifiers only as necessary to confirm participant eligibility and document procedures and follow-up visits.*

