PROTOCOL TITLE: “Evaluating the efficacy of micro-fragmented adipose tissue and intra-articular corticosteroid injections for symptomatic knee osteoarthritis: a randomized, placebo controlled study”

- 16.3. The research team will have access to the patient’s PHI, as data may be needed from their consultation visits prior to enrollment in the study. Furthermore, they will have access to the medical record as procedures and follow-up visits will be documented in their medical records.
- 16.4. Not applicable. The study team may only know of any sensitive PHI if noted in medical chart.
- 16.5. Not applicable.
- 16.6. Participants will fill out questionnaire at their procedure and their 6 week and 6 month visits. These questionnaires will be filled out on paper and will only have the participant’s unique identifier number on them. The data will be entered into RedCap by a member of the research staff. These paper copies will be kept in a locked file cabinet in [name]’s office behind a locked door. In addition, each participant will be assigned a number from 001-100. This code will be kept on a password protected excel file on [name]’s password protected computer located in his office behind a locked door. Only the PI and research staff will have access to any of these documents. No data is to be transported or transmitted to any other computer or location. Participants will also complete the questionnaires via RedCap (or phone if the patient doesn’t have email or internet access) at 2 weeks, 3 months, and 1 year post injection. If a patient has internet access and email, surveys will be sent and completed securely via RedCap. If performed by phone, the member of the research staff will collect the data on paper and it will then be transcribed into RedCap.
Data will be kept for one year after full completion of data collection to allow time for data analysis and manuscript writing. Paper files, such as consent forms and questionnaires, will be appropriately shredded and disposed of. Excel files will be deleted. As no additional copies will be stored, this will destroy all of the identifiers and excel logs.
- 16.7. Each participant will be assigned a number from 001-100. This code will be kept on a password protected excel file on [name]’s password protected computer located in his office behind a locked door. There will only be patient names and unique identification numbers on this document. Only the PI and research staff will have access to the document.

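### Section 15.1 withdraws participants who miss or do not schedule visits without keeping the questionnaires that need no visit; the loss is probably small, but cheap to avoid

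*Combined protocol and SAP*

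**What the plan says.** Section 15.1, on withdrawal from the study, is mandatory in form: "If participants are not adherent and miss follow-up appointments, refuse to be scheduled, or do not respond to scheduling requests, they will be withdrawn". It does not say how many missed appointments are needed, or what happens to the questionnaires still due.

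Section 15.3 provides a lesser step: "Partial withdrawal will be permitted if a patient desires to continue participating in data collection but no longer wishes to be seen for follow-up". It adds: "The questionnaires would be completed online only". Neither section refers to the other.

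On data, section 15.4 says that after a withdrawal "all previously collected data will still be used for statistical analysis" unless the participant objects, and section 15.5 says that "data that was collected prior to withdrawal from the study may be used for analysis". Neither mentions data that could be collected afterwards.

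Under section 12.1, item 5, only the 6-week and 6-month assessments are tied to a visit. For the other three: "They will also complete the above surveys and log at 2 weeks, 3 months, and 1 year post injection, but these will be completed online". There is a fallback: "If participants do not have email or access to the internet, these surveys will be completed over the phone". Section 16.6 repeats both modes.

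Sections 5.3 and 13.1 plan mixed-effects models on five repeated measurements. Section 5.3 gives no drop-out rate and expects the model to make up for drop-out.

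**The concern.** The pain and function outcomes are all self-completed questionnaires, so a missed visit need not cost any later outcome data. As written, 15.1 treats failing to attend and ceasing to provide data as one event. Someone who simply misses a visit or does not answer has expressed no wish to continue without visits, so 15.3 does not reach them and 15.1 does. Someone who refuses to be scheduled could fall under either section, and nothing says which is tried first.

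At stake is avoidable loss of late follow-up, above all the 1-year survey, in a trial that section 5.2 says needs 75 completers.

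**Working it through.** **Assessments lost if 15.1 ends data collection** (schedule in 12.1)
- Withdrawal at a missed 6-week visit loses 4 of 5 post-injection assessments: 6 weeks, 3 months, 6 months and 1 year. Two of these need no visit.
- Withdrawal at a missed 6-month visit loses 2 of 5: 6 months and 1 year. One needs no visit.
- Either way the 1-year survey is lost.

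**The plan's own figure.** Sections 5.3 and 13.2 adopt 22 per group for 15 points, SD 20, 80% power and 5% type I error, without stating sidedness. With n = 2(SD/difference)²(z_α + z_β)²:
- one-sided: 2 × (20/15)² × (1.645 + 0.842)² = 22.0, a match;
- two-sided: 2 × (20/15)² × (1.960 + 0.842)² = 27.9, so 28, no match.

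**Inputs for the effect of withdrawal.** From the documents: five follow-ups, 25 per arm, 15 points, SD 20, 5%. Assumed, because the documents give no values: probability p of missing each visit (10%, range 5–15%), correlation 0.6 between any two time points (range 0.4–0.8), and the share who return later surveys. I use two-sided tests unless stated. Power is Φ(difference/SE − z), with the SE from generalised least squares, summing information over the missingness patterns.

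**Complete data**
- 1 year: SE = √(2 × 20²/25) = 5.66; 15/5.66 − 1.96 = 0.69; power 75.5%.
- Average of five: SE = √(2 × 20² × (1 + 4 × 0.6)/(5 × 25)) = 4.66; 15/4.66 − 1.96 = 1.26; power 89.5%.

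**Reading (a): one miss triggers withdrawal.** Withdrawn = 1 − (1 − p)².

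| p | Withdrawn | Of 75 | Power at 1 year |
|---|---|---|---|
| 5% | 9.75% | 7.3 | 73.0% |
| 10% | 19% | 14.2 | 70.2% |
| 15% | 27.75% | 20.8 | 67.1% |

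At p = 10%:
- Correlation 0.4 or 0.8 gives 68.3% or 72.6% at 1 year.
- If 25%, 50% or 100% of those otherwise withdrawn return later surveys, 1-year power is 71.7%, 73.1% or 75.5%. A return of 25–50% thus recovers 1.5 to 2.9 points.
- Averaged over follow-up, power is 88.2% under the rule and 89.4% with full return of later surveys, a difference of 1.2 points. The 89.4% counts the missed visit's own questionnaire as lost; if that is returned too, power is the complete-data 89.5%.
- One-sided, 1-year power goes from 84.3% to 80.1%.

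**Reading (b): half of misses are refusals or non-responses that trigger at once (assumed); the rest count only if both visits are missed.** At p = 10%, withdrawn = 0.05 + 0.05 × 0.10 + 0.90 × 0.05 = 10%, or 7.5 of 75. Power is 72.9% at 1 year and 88.8% averaged.

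**Reading (c): both visits must be missed.** Withdrawn = 0.10² = 1%. Power is 75.3% at 1 year and 89.3% averaged, against 75.5% and 89.5% with complete data.

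**The case against.** The strongest reply is that the effect is small and partly covered already. Much of it stands.

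- **One miss is not the plain trigger.** The text joins non-adherence with missed appointments in the plural, only two visits exist, and section 6.1 allows flexible scheduling. Reading (a) is therefore an upper bound. Refusal and non-response carry no count, however, so (c) is not assured either.
- **One year is not named as primary.** The sample size rests on an average change over time, and on that measure even (a) costs about 1 point.
- **15.3, 15.4 and 15.5 help.** Patients who want to continue can, and earlier data stay in the model. What remains uncovered is people who miss visits or do not reply and express no wish.
- **Visits serve monitoring.** Sections 14.1 and 14.2 use the follow-up visits to watch for adverse reactions, so requiring attendance is a coherent choice. That is a reason to keep the visits, not to stop the questionnaires.

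Four stronger inferences are tempting but unsupported:
- That the plan expressly stops the surveys. No sentence says so.
- That 15.1 pushes power below 80%. The two-sided 1-year figure is 75.5% before anyone is withdrawn, which is a separate sample-size matter. On the one-sided basis that reproduces 22, reading (a) still gives 80.1%.
- That phone participants have no route once visits stop. The words in 15.3 can be read that way, but with the standing phone fallback in 12.1 and 16.6 they more naturally mean not in person.
- That the rule biases the comparison. The documents give no basis for a differential withdrawal rate or its relation to outcome.

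**Conclusion.** The gap is real and minor: a cheap improvement. Section 15.1, read naturally, discards questionnaires that the trial could still collect, and 15.3 does not repair this because it depends on an expressed wish and is not linked.

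The cost in power runs from negligible, if both visits must be missed, to about 1 point averaged over follow-up and 5 points at 1 year, if one miss suffices. These sizes rest on the assumed 10% miss rate and 0.6 correlation. Full recovery would need every such participant to return later surveys, which is unlikely among people who did not answer staff. Rebooked visits, or enrolment above 25 per arm as 5.3 permits, would shrink the effect further.

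**What to change.** Reword 15.1 so that missing or not scheduling a visit ends visits only, not data collection. Suggested text:

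> The questionnaires for the missed visit and all later time points are still sent through RedCap, or completed by phone where there is no email, internet or reply, unless the participant withdraws consent for data collection.

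Then:
- state that the 15.3 option is offered before any withdrawal is recorded;
- in 15.3, allow completion online or by phone, and extend the phone route in 12.1 and 16.6 to people who do not reply. Section 16.6 now says "If a patient has internet access and email, surveys will be sent and completed securely via RedCap", with phone only for those without access;
- because 25.1.5 confirms willingness to continue at visits, ask the same question at the start of the survey or call when a visit is missed;
- leave the visit schedule and the visit-based monitoring in 14.1 and 14.2 unchanged.

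The cost is wording, some reminders and a little phone and data-entry time. At 10% missed under reading (a), 0.10 × 75 = 7.5 people have 4 questionnaires outstanding and 0.90 × 0.10 × 75 = 6.75 have 2. That is 7.5 × 4 + 6.75 × 2 = 43.5 contacts at most over the whole trial. Of these, 7.5 × 2 + 6.75 × 1 = 21.75 are 3-month and 1-year surveys already scheduled as remote. No visits are added.

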1. Participants will be screened prior to enrollment. Depending on their medical history and prior consultations, they will likely have a physical exam and x-rays of the affected knee(s). This is standard of care and will happen prior to enrollment in the study. X-ray images and medical data from these visits may be used for the purposes of analyzing statistical data.

PROTOCOL TITLE: "Evaluating the efficacy of micro-fragmented adipose tissue and intra-articular corticosteroid injections for symptomatic knee osteoarthritis: a randomized, placebo controlled study"

2. Upon enrollment, participants will be randomized to a treatment group and scheduled for their injection procedure.
3. At their injection visit, participants will complete the Western Ontario and McMaster Universities Osteoarthritis Index, a Visual Analog pain scale, and the Knee Injury and Osteoarthritis Outcome Score scales to establish a baseline. They will also fill out a medication log to document any medications that they take, including oral pain medications, although we will not be intervening with oral medications. They will complete these surveys and the log again at 2 weeks, 6 weeks, 3 months, 6 months, and 1 year after the injections

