- 13.2. *Since patient perception of post-treatment pain as measured by the VAS scale is a main variable of interest in our hypothesis, we searched the literature for previous studies in which the variability of pain using a VAS scale was investigated.²⁰⁻²³ We estimated that the standard deviation likely to be found for our own observations will be approximately 35 on a 100 point scale, conservatively. We assume that most clinicians will consider a difference in post-treatment pain of about 15 points to be clinically important, as supported by Tashjian et al, who estimated 1.4 cm as the minimal clinically important difference on a 10 cm scale. To determine an adequate sample size for our pilot, we assumed average change in pain score over the follow-up to be 10-15, and standard deviation to be 10-20. To have 80% power with a 5% Type I error an approximate 2-way ANOVA model suggest sample size in the range of 18-49 per group. We adopt n=22 as our minimum sample size per group based on the assumption of 15-point change in pain score over time on average and a 20-point standard deviation over time.*

14. Provisions to Monitor the Data to Ensure the Safety of Subjects

- 14.1. *Corticosteroids are standard of care. Lipogems® is approved for use in orthopaedics and arthroscopic procedures. Participants will be closely followed by the participating clinicians/investigators through the follow-up visits required for participation. All measures will be taken to ensure that participants receive appropriate care.*
- 14.2. *Patients will be informed of the risks of participating prior to enrolling in the study and may choose to enroll or not enroll. They will be reminded of expected post-procedural findings and will be monitored for adverse reactions by the participating clinicians at their follow-up visits.*
- 14.3. *The data monitoring committee will consist of [name], [name] [Orthopaedic Sports Medicine], [name] [Orthopaedic*

PROTOCOL TITLE: “Evaluating the efficacy of micro-fragmented adipose tissue and intra-articular corticosteroid injections for symptomatic knee osteoarthritis: a randomized, placebo controlled study”

Sports Medicine]; this committee will conduct a preliminary review of the existing data once 10 participants have been enrolled in each group.

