- 16.8. Not applicable. As participants will be answering questionnaires and filling them out on their own, there is no need for quality control.
- 16.9. Not applicable. Data will not be transferred or transmitted to outside locations or entities. Any paper copies of questionnaires will be collected within CTSC facilities and will be input into RedCap. Paper copies will be stored as outlined in this protocol.
- 16.10. There will be data collected via a secure RedCap survey. Participants will be emailed a link to complete the questionnaires. This secure email will be sent

PROTOCOL TITLE: “Evaluating the efficacy of micro-fragmented adipose tissue and intra-articular corticosteroid injections for symptomatic knee osteoarthritis: a randomized, placebo controlled study”

through RedCap and all data will be gathered through RedCap. RedCap is a secure web application frequently utilized to collect data for research, including HIPAA compliant information.

16.11. *Not applicable. Data will not be collected by audio or video recording.*

16.12. *Not applicable. No photographs of participants will be taken at any point during the study.*

17. Data and Specimen Banking

17.1. *Not applicable. There will not be any data or specimen banking.*

17.2. *Not applicable. This is not a multi-center study, nor will any data or specimens be banked.*

18. Risks to Subjects

18.1. *This study involves risks to the participants as corticosteroids and Lipogems® are both used by clinicians as part of the current standard of care for knee osteoarthritis. One potential risk that may arise is a breach in patient confidentiality. Although such a breach is unlikely to occur and should not negatively impact patient health or well-being, we will take precautions to minimize this risk. All investigators and members of the study team will strictly adhere to the HIPAA and patient confidentiality guidelines set forth by the hospital. All research staff will adhere to the guidelines set forth in the Data Management/Confidentiality portion of this protocol.*

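### Section 16.8 waives quality control because participants complete the forms themselves, but staff key about half of the assessments from paper and no check of those entries is described

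*Combined protocol and SAP*

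**What the plan says.** Section 16.8 declares quality control not applicable. Its only ground is self-completion: "As participants will be answering questionnaires and filling them out on their own, there is no need for quality control".

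Section 16.6 describes how the data reach the database. On timing: "Participants will fill out questionnaire at their procedure and their 6 week and 6 month visits". On medium: "These questionnaires will be filled out on paper". On entry: "The data will be entered into RedCap by a member of the research staff". Section 16.9 repeats that paper copies are input into RedCap.

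At 2 weeks, 3 months and 1 year the surveys are online. Participants without email or internet answer by phone, and then "the member of the research staff will collect the data on paper and it will then be transcribed into RedCap".

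On retention, 16.6 keeps the data for one year after data collection is complete, to cover analysis and writing. After that: "Paper files, such as consent forms and questionnaires, will be appropriately shredded and disposed of".

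The scores concerned are VAS pain, WOMAC and KOOS. Section 13.2 says that "patient perception of post-treatment pain as measured by the VAS scale is a main variable of interest in our hypothesis".

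**The concern.** Completing a form oneself says nothing about whether someone else later types the answers in correctly. The reason in 16.8 would fit a trial in which participants enter everything directly. It does not fit the manual step that 16.6 creates. This is therefore a stated rule resting on a premise that another section contradicts, not merely a missing detail.

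The scores at stake are the trial's outcomes. Every baseline is on paper, and the sample size in 13.2 is framed as change in pain score, so one mistyped baseline would affect all five of that participant's change values. In a trial of about 25 per arm, a few gross errors add noise and dilute the difference between arms. Any check has to happen while the paper still exists, and none is scheduled.

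**Working it through.** The plan gives no entry-error rate and no figure for data quality, so there is nothing of its own to reproduce. The check has three parts.

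**1. How much is keyed by staff**

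Inputs: 75 completers (5.2); baseline at the injection visit plus five follow-ups, so six time points (12.1: "They will complete these surveys and the log again at 2 weeks, 6 weeks, 3 months, 6 months, and 1 year after the injections"); three of the six on paper (16.6).

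- All sets: 75 x 6 = 450. Paper sets: 75 x 3 = 225, or 50%.
- The share answering by phone is not stated. If it is 10% to 30% (assumption), phone adds 22.5 to 67.5 sets, giving about 248 to 293 of 450 (55% to 65%).
- Section 15.3 lets partial withdrawals answer online only, which lowers the 6-week and 6-month counts a little.

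**2. Whether any other provision checks the entries**

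- Section 9.3 has staff trained in data collection and gives access to CTSC coordinators and statisticians.
- Section 14.3 has one preliminary data review once 10 participants are enrolled in each group.

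Neither is described as comparing entries with the paper. No double entry, range check, source audit or query process appears.

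**3. What errors would cost**

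Assumptions: a share e of entered VAS values is replaced by a value uniform on 0 to 100 (mean 50, variance 833), and true scores have mean 40. The 15-point difference and SD of 20 come from 13.2 and the 25 per arm from 5.3. The test is a two-sided 5% two-sample t-test.

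- Difference: 15(1 - e)
- Variance: 400(1 - e) + 833e + 100e(1 - e)

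Without errors, the noncentrality is 15 / (20 x sqrt(2/25)) = 2.65 on 48 degrees of freedom, so power is 73.8%. (The normal approximation gives 75.5%.)

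At e = 3%, the difference is 14.55, the variance is 388 + 25 + 2.9 = 415.9 and the SD is 20.4. Noncentrality is 2.52 and power is 69.6%.

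| Error rate | Expected wrong values in 225 | Power, single paper visit |
|---|---|---|
| 0 | 0 | 73.8% |
| 0.5% | 1.1 | 73.1% |
| 1% | 2.3 | 72.4% |
| 2% | 4.5 | 71.0% |
| 3% | 6.8 | 69.6% |
| 5% | 11.3 | 66.7% |

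That column applies only to a comparison at 6 weeks or 6 months. The main analysis in 13.1 uses all five follow-ups, of which two are on paper. For their average, with equal correlation rho between visits (assumed 0.3 to 0.9) and no phone entries, the difference is 15 x (3 + 2(1 - e))/5. At e = 3% this is 14.82.

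With rho = 0.5, the variance of the average goes from 240 to 237.5. Rescaled to the same 73.8% start, the noncentrality is 2.65 x (14.82/15) x sqrt(240/237.5) = 2.63, and power is 73.3%.

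Over rho 0.3 to 0.9:

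- 3% errors: 73.1% to 73.5%, a loss under 1 point.
- 5% errors: 72.5% to 73.2%, a loss under 1.5 points.

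This calculation uses follow-up scores only. Change-from-baseline scores or phone entries would raise the loss somewhat and are not modelled.

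For scale, one uncaught 45-point slip moves the mean of a 25-person arm at that visit by 45/25 = 1.8 points, and a 90-point slip by 3.6, against a 15-point difference of interest.

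**The case against.** The strongest reply is that the numerical harm is slight and the error rate is not in the documents. Both are true. The plan's mixed model spreads two paper follow-ups over five. The uniform-replacement model is also harsh, since a digit slip need not be unrelated to the true score. Training and one committee look at the data offer some general protection, although neither is described as entry verification.

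Three stronger readings are tempting, and the documents do not support them:

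- **Errors cannot be corrected at all.** A reader might infer this from the shredding. But 16.6 keeps data for a year after collection ends, so paper and database could be compared throughout the analysis period. What is missing is a scheduled check, not the opportunity for one.
- **Data-entry staff are unblinded, so errors could favour an arm.** Sections 27.1 and 28.2 call the trial single-blinded with reference to participants. Whether the person keying knows the arm is not stated. The paper forms carry only an identifier (16.6), and the code file holds only names and numbers (16.7).
- **Staff must measure a mark on a VAS line.** The layout of the paper VAS is not described, and the same scale is also given by phone.

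What remains is that the stated reason for the waiver is wrong for about half the data, and that nothing takes the place of the waived control.

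**Conclusion.** The point holds as an inconsistency between 16.8 and 16.6 that leaves staff-keyed outcome data without any described verification. It covers about 225 of 450 assessment sets, including every baseline; phone answers add to this and partial withdrawals reduce it slightly.

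The likely statistical cost is small. Under an assumed 3% random error rate it is about 4 points of power for a single paper visit and under 1 point for the average over five follow-ups. These sizes rest on the assumed error rate and error model, the 15-point difference, SD 20 and 25 per arm. The 73.8% is a benchmark for measuring the loss, not a judgement on the plan's sample size. No claim of bias between arms is made. This is a worthwhile, low-cost improvement and not a threat to the trial's conclusions.

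**What to change.** Replace 16.8 with a stated check. Either route would do:

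- **Keep paper and verify.** A second existing staff member compares every paper or phone VAS, WOMAC and KOOS entry with its source, or the entries are keyed twice. RedCap range checks are switched on. Discrepancies are resolved and recorded before analysis. Section 16.6 then makes completion of this check a condition for shredding.
- **Remove the transcription.** At the procedure, 6-week and 6-month visits participants enter their answers directly in the RedCap surveys that 12.1 already provides for the other time points, with range checks and paper as backup only. Remaining paper and phone entries get the second check above. This also makes the mode of completion nearly uniform across visits. Sections 16.6 and 16.9 would need matching edits.

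The first route costs a modest amount of existing staff time. The second needs a clinic device, and some participants may need help using it. Neither changes a treatment, a visit or an endpoint.
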